13.2.4 Exploratory Analyses

For the analyses involving score changes, the investigators will use ANCOVA in place of 2-sample t-tests, which has been found to be robust to violation of modeling assumptions.

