4 STUDY DESIGN

4.1 Description

This is a Phase 2, double-blinded, placebo-controlled trial assessing the safety of Q-Urol use after brachytherapy placement in patients with localized prostate cancer. Patients will be randomized in a 1:1 ratio to receive Q-Urol/Placebo twice daily for six weeks after brachytherapy placement. Questionnaires will be administered pre- and post-treatment to assess the change in prostatitis symptoms and quality of life measures. The mean values between groups will be compared.

Once 42 patients (21 to each arm) have been enrolled and treated on the study therapy, enrollment will be placed on hold and an interim analysis conducted. The interim analysis will be conducted for futility and efficacy and will be reviewed by the DSMC. If the analysis is favorable, as defined in the Statistical Analysis section, the trial will open to the enrollment of 98 additional subjects, 49 per arm. However, if the analysis does not demonstrate standards defined in the statistical analysis, the trial will be closed to accrual.

Version Date: 11APR2023

Safety monitoring will be overseen by the DSMC at HCI. See Section 12.4 for safety monitoring plan and early stopping rules.

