4.3 Number of Patients

The trial will enroll up to 70 patients to each arm, 140 patients total.

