11.5 Questionnaire administration

All questionnaires will be completed in the clinic by the patient prior to starting study therapy and after completing six weeks of daily Q-Urol/Placebo therapy.

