13.2 Statistical Analyses

13.2.1 Sample size determination

The outcome for sample size determination is the primary endpoint variable, the peak of the National Institutes of Health-Chronic Prostatitis Symptom Index (NIH-CPSI) total score measured from baseline to six weeks post brachytherapy. The primary hypothesis is that the mean of the primary outcome variable will be $\frac{1}{2}$ standard deviation lower in patients taking Q-Urol compared to placebo. A single interim analysis is planned after N1= 21 subjects per group have outcome data. The interim and final analysis will compare the treatment and control means using nominal t statistics (control minus treatment). If the t statistic has a value less than -1.16 at the interim analysis the trial will be terminated for futility. If the t statistic has a value greater than 2.85 at the interim analysis the trial will be terminated for efficacy.

If the study is not terminated for efficacy or futility at the interim analysis an additional N2 = 49 patients per group will be accrued for a total of N = 70 patients per group. If the interim analysis is done at the planned sample size (21 patients per group) the treatment will be deemed efficacious at the final analysis if the t statistic has a nominal value greater than 1.67.

The above design was evaluated using 100,000 simulated data sets for both the null and alternative hypotheses. There is 90% power at overall one-sided Type I error equal to 0.05 (one-sided) to detect a 0.5 standard deviation lower mean of the primary endpoint in the treatment group compared to the control group. The probability of early termination for futility under the null hypothesis is 12%. The probability of early termination for futility under the alternative hypothesis is 0.3%. The probability of early termination for efficacy under the alternative hypothesis is 12%.

If the interim analysis or final analysis is performed at a sample size that is different than the planned sample size the final analysis will be adjusted to maintain an overall Type I error of no more than 0.05 (one-sided).

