13.2.3 Secondary endpoint

- 1. Patient questionnaires administered pre- and post-study therapy: The Expanded Prostate Cancer Index Composite (EPIC), The International Prostate Symptom Score (I-PSS), The Rectal Function Assessment Score (R-FAS), and the Sexual Health Inventory for Men (SHIM). The change in questionnaire scores will be compared between groups using two-sample *t*-tests. If normality assumptions are violated, non-parametric Wilcoxon tests may be used. Confidence intervals for the mean change between and within groups will also be reported.
- 2. Inflammation markers pre and post brachytherapy: erythrocyte sedimentation rate, C-reactive protein, and prostate-specific antigen (PSA). The change in inflammatory markers will be compared between groups using two-sample t-tests. If normality assumptions are violated, non-parametric Wilcoxon tests may be used. Confidence intervals for the mean change between and within groups will also be reported. For laboratory markers that are known to be positivity skewed, such as CRP, the analyses will be based on the log-transformed values.
- 3. The frequency of adverse events (AEs) will be collected and characterized by type, severity (as defined by CTCAE, version 5.0), seriousness, duration, and relationship to study treatment. Counts and proportions of patients with adverse events will be tabulated and exact 95% binomial confidence intervals will be reported.
- 4. The number of days during the 28 days post-brachytherapy that any medication is taken for the treatment of prostate-related pain will be summarized using the mean, median and interquartile range. A Wilcoxon test will be used to compare the arms.

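### The secondary questionnaire analysis gives the unadjusted t-test on change higher status than ANCOVA, and 13.2.4 leaves the relation between the two unclear and names no covariate

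*Combined protocol and SAP*

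**What the plan says.** Objective 1.2.1 (quality of life by domain) rests on four questionnaires: EPIC, I-PSS, R-FAS and SHIM. Section 13.2.3 item 1 gives their analysis: "The change in questionnaire scores will be compared between groups using two-sample" t-tests. A rank test is an optional fallback ("If normality assumptions are violated, non-parametric Wilcoxon tests may be used"), and confidence intervals for mean change between and within arms are promised.

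The next section, headed "13.2.4 Exploratory Analyses", consists of one sentence. It says "For the analyses involving score changes, the investigators will use ANCOVA in place of 2-sample t-tests" and gives robustness to violated modelling assumptions as the reason. It names no covariate and no outcome form (change or end-of-treatment score). It does not say which result is reported for the secondary endpoint.

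The data needed for adjustment are already planned. Section 11.5 says "All questionnaires will be completed in the clinic by the patient prior to starting study therapy and after completing six weeks" of study therapy, so each patient should have one baseline and one end-of-treatment value on every scale.

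**The concern.** Two sections assign different tests to the same score changes. Their headings rank the t-test above ANCOVA, but the wording of 13.2.4 has ANCOVA taking the t-test's place. An analyst could defend either as the planned secondary analysis, and should not have to choose once unblinded results are visible.

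The ranking is also the wrong way round for efficiency. A change score subtracts the baseline with a fixed coefficient of 1, whereas ANCOVA estimates that coefficient. Unless the true within-arm slope is 1, the change score carries avoidable variance, including part of any chance baseline imbalance. At stake are the precision of the quality-of-life results and a clear statement of which estimate is the secondary result.

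**Working it through.** **Reproducing the plan's own figure.** The only stated power is for the primary endpoint: "There is 90% power at overall one-sided Type I error equal to 0.05 (one-sided) to detect a 0.5 standard deviation lower mean". Simulating 200,000 trials under each hypothesis, with looks at 21 and 70 per arm and boundaries -1.16, 2.85 and 1.67, gives power 90.0% and one-sided type I error 0.04996. Futility stopping is 12.5% under the null (stated 12%) and 0.3% under the alternative (stated 0.3%). Efficacy stopping under the alternative is 12.5% (stated 12%). The primary design reproduces. No power or alpha is stated for any secondary endpoint.

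**Inputs for the secondary comparison**

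- Sample size: 70 per arm, allocated 1:1 (4.3: "The trial will enroll up to 70 patients to each arm, 140 patients total"; ratio in 4.1).
- Effect: 0.5 baseline SD, the minimal important difference set in 2.5 for each patient-reported measure.
- Assumed, because the documents are silent: two-sided 5%; baseline score as the ANCOVA covariate; pre-post correlation r of 0.3, 0.5 or 0.7; post/pre SD ratio s of 1, 1.25 or 1.5.

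**Formulas**, in units of baseline variance:

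- Change score: Vc = 1 + s² − 2rs
- ANCOVA residual: Va = s²(1 − r²)
- Difference: Vc − Va = (1 − rs)², which is never negative and is zero only when the within-arm slope rs equals 1
- With s = 1 the ratio Va/Vc is (1 + r)/2: 0.65, 0.75 and 0.85 at the three correlations
- Power: noncentral t with noncentrality 0.5/√(2V/70), on 138 df for the t-test and 137 df for ANCOVA

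**Worked cases at r = 0.5**

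- s = 1: Vc = 1 + 1 − 1 = 1.00 and Va = 0.75. Noncentralities are 0.5/√(2/70) = 2.958 and 0.5/√(1.5/70) = 3.416. Power is 83.6% versus 92.4%.
- s = 1.5: Vc = 1 + 2.25 − 1.5 = 1.75 and Va = 2.25 × 0.75 = 1.6875. Noncentralities are 2.236 and 2.277. Power is 60% versus 62%.

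**Power, t-test on change / ANCOVA**

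| Post/pre SD ratio | r = 0.3 | r = 0.5 | r = 0.7 |
|---|---|---|---|
| 1 | 70% / 87% | 84% / 92% | 97% / 98% |
| 1.25 | 59% / 69% | 73% / 77% | 90% / 91% |
| 1.5 | 48% / 54% | 60% / 62% | 78% / 78% |

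Simulation of 5,000 trials per correlation confirms the equal-SD row: 69.7/86.8%, 83.7/92.6% and 96.7/98.5%. In a separate simulation of 20,000 trials per setting, each test alone rejected in 4.7–5.0% of trials under no effect.

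**The case against.** The strongest reply is that the headings already settle the hierarchy: the t-test is under the secondary endpoint, ANCOVA is under exploratory analyses, and 13.2.4 merely describes an exploratory re-analysis. That is the most natural reading, so a reader who infers a flat contradiction goes too far. What survives is that the wording of 13.2.4 fits this reading poorly, and that under it the ANCOVA is still unspecified and the less efficient test still ranks higher.

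Second, the t-test on change is a valid randomised comparison. This stands. Both tests hold their level and target the same mean treatment difference. Chance baseline imbalance adds variance, not bias over repeated randomisation.

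Third, the large gains belong to the equal-SD case. This also stands. Section 5.2.1 excludes baseline AUA scores above 15, and 2.1 says symptoms affect virtually all patients and peak around weeks 4–6. A larger post-treatment SD is therefore plausible for the urinary scores, though no SDs are given. At a ratio of 1.5 the gain is 6 points or less.

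Two further inferences are tempting but unsupported. One is that the tests could reach opposite conclusions. In simulation with equal SDs and a 0.5 SD effect, they differ on significance in 20%, 11% and 2% of trials at the three correlations. That is one p-value on each side of 0.05, not opposite directions, and it mostly restates the power gaps of about 17, 9 and 2 points. The other is that objective 1.2.1 depends on these tests alone: 13.2.3 also commits to confidence intervals, and 2.5 supplies a half-SD difference for interpreting them.

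**Conclusion.** The point holds as one of analysis hierarchy and efficiency. Section 13.2.3 gives secondary status to the unadjusted t-test on change. Section 13.2.4 proposes ANCOVA in terms that do not fit an exploratory supplement and leaves the model undefined. With baseline as covariate, ANCOVA costs one degree of freedom and is otherwise never less precise. Its power gain runs from about 17 points (equal SDs, correlation 0.3) to essentially nil (SD ratio 1.5, correlation 0.7).

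These figures assume 70 per arm, a 0.5 baseline-SD effect and two-sided 5%; the correlations and SD ratios are assumptions, not values from the documents. The documents do not support calling the t-test invalid, or quoting a single power loss without that range. Nothing here touches the primary test, its boundaries or the sample size.

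**What to change.** In 13.2.3 item 1, name ANCOVA as the secondary analysis for each questionnaire score: end-of-treatment score as outcome, arm and that score's own baseline value as covariates, and the adjusted mean difference with its 95% confidence interval as the reported result. Label the two-sample t-test on change as supportive. Reword 13.2.4 to match, or delete it.

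The cost is about one paragraph of text. Baseline scores are already collected, so no visits, patients or data are added, and type I error is not affected. The change should be made before unblinded data are analysed.

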14 REGISTRATION GUIDELINES

Study-related screening procedures can only begin once the patient has signed a consent form.

Patients must meet all of the eligibility requirements listed in Section 5 prior to registration.

Patients must be registered before receiving any study treatment and must begin treatment as soon as logistically possible after registration.

To register eligible patients on study, complete a Clinical Trials Office Patient Registration Form and submit to [contact].

Version Date: 11APR2023

15 DATA SUBMISSION SCHEDULE

The Case Report Forms (CRFs) are a set of (electronic or paper) forms for each patient that provides a record of the data generated according to the protocol. CRF's should be created prior to the study being initiated and updated (if applicable) when amendments to the protocol are IRB approved. These forms will be completed on an on-going basis during the study. The medical records will be a source of verification of the data. During the study, the CRFs will be monitored for completeness, accuracy, legibility and attention to detail by a member of the Research Compliance Office. The CRFs will be completed by the Investigator or a member of the study team as listed on the Delegation of Duties Log. The data will be reviewed no less than annually by the Data and Safety Monitoring Committee. The Investigator will allow the Data and Safety Monitoring Committee or Research Compliance Office personnel access to the patient source documents, clinical supplies dispensing and storage area, and study documentation for the above-mentioned purpose. The Investigator further agrees to assist the site visitors in their activities.

Data capture should be restricted to endpoints and relevant patient information required for planned manuscripts.

16 ETHICAL AND REGULATORY CONSIDERATIONS

16.1 Human Subject Protections

The study will be conducted in accordance with the appropriate FDA, IRB, ICH GCP, and other federal and local regulatory requirements, as applicable. Informed consent will be obtained from all research participants prior to performing any study procedures using the most recent IRB-approved version. All patients must be at least 18 years of age to participate.

16.2 Institutional Review

Before study initiation, the investigator must have written and dated approval/favorable opinion from the IRB/IEC for the protocol, consent form, subject recruitment materials (e.g., advertisements), and any other applicable patient-facing documents. The investigator should also provide the IRB/IEC with a copy of the Investigator Brochure or product labeling information.

The investigator or designee should provide the IRB/IEC with reports, updates, and other information (e.g., expedited safety reports, amendments, and administrative letters) according to regulatory requirements or institution procedures.

16.3 Data and Safety Monitoring Plan

A Data and Safety Monitoring Committee (DSMC) is established at Huntsman Cancer Institute (HCI) to ensure the well-being of patients enrolled on Investigator Initiated Trials that do not have an outside monitoring review. The roles and responsibilities of the DSMC are set forth in the NCI-approved Data and Safety Monitoring (DSM) plan. The activities of the committee include reviewing adverse events (including SAEs), deviations, important medical events, significant revisions or amendments to the protocol, and approving cohort/dose escalations. If the DSMC and/or the PI have concerns about unexpected safety issues or rising AE trends, the study will be stopped and an unplanned safety data analysis

Version Date: 11APR2023

may take place. Enrollment will not resume until the issues are resolved. The DSMC also reviews and approves audit reports generated by the Research Compliance Office.

This is a Phase II study holding an IND and is classified as high risk per the NCI-approved DSM plan.

Each high-risk study will be assigned a physician member of the DSMC as a medical monitor, or in rare cases, an external medical monitor. The medical monitor will be notified of all serious adverse events (SAEs). All serious adverse events (SAEs) occurring in patients treated at HCI or its affiliates will also be reviewed by the full DSMC monthly.

Each high-risk study will also be assigned a dedicated research compliance officer who will monitor the trial. High-risk studies will be monitored by RCO personnel after the first patient is enrolled and every three months thereafter during active enrollment. The RCO monitor will review the study status and summarize enrollment, toxicities, SAEs, dose-escalation, statistical endpoints (e.g., stopping rules), deviations, etc. for the full DSMC membership at the regularly scheduled meetings. Amendments that increase risk, change dosing, or impact study objectives will be reviewed by the DSMC and approved by the PRMC and IRB. High-risk trials will be formally reviewed by the DSMC after the first patient is enrolled and then quarterly thereafter.

An initial audit of high-risk studies will be conducted by the RCO approximately one year after enrollment begins and annually thereafter. Audits of high-risk studies may be conducted more frequently as requested by the DSMC, IRB, PRMC, RCO management, or the PI.

16.4 Adverse Events and Serious Adverse Events

This study will utilize the CTCAE (NCI Common Terminology Criteria for Adverse Events) Version 5.0 for AE and SAE reporting.

16.4.1 Adverse Events (AEs)

An adverse event is the appearance or worsening of any undesirable sign, symptom, or medical condition occurring after starting the study drug even if the event is not considered to be related to the study drug. For the purposes of this study, the terms toxicity and adverse event are used interchangeably. Medical conditions/diseases present before starting study drug are only considered adverse events if they worsen after starting the study drug. Abnormal laboratory values or test results constitute adverse events only if they induce clinical signs or symptoms, are considered clinically significant, or require therapy.

The collection of adverse events will begin after the study drug has been started and end 30 days after the last dose study drug (or until new cancer treatment is initiated).

Information about all adverse events, whether volunteered by the subject, discovered by investigator questioning, or detected through physical examination, laboratory test, or other means, will be collected, recorded, and followed as appropriate.

The adverse event should be evaluated to determine:

1. The severity grade based on CTCAE v5.0 (grade 1-5)

Version Date: 11APR2023

2. Its relationship to the study drug, brachytherapy, and ADT (definite, probable, possible, unlikely, not related)

- 3. Its duration (start and end dates or if continuing at the final exam)
- 4. Action taken (no action taken; study drug dosage adjusted/temporarily interrupted; study drug permanently discontinued due to this adverse event; concomitant medication taken; non-drug therapy given; hospitalization/prolonged hospitalization)
- 5. Whether it constitutes an SAE

All adverse events will be treated appropriately. Such treatment may include changes in study drug treatment as listed in the dose modification section of this protocol (see section 8 for guidance). Once an adverse event is detected, it should be followed until its resolution, and assessment should be made at each visit (or more frequently, if necessary) of any changes in severity, the suspected relationship to the study drug, the interventions required to treat it, and the outcome.

Information about common side effects already known about Q-Urol is described in the Drug Information (Section 3). This information will be included in the patient informed consent and will be discussed with the patient during the study as needed.

All adverse events will be immediately recorded in the patient research chart.

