8 TOXICITIES AND DOSE MODIFICATION

Every effort should be made to administer Q-Urol/Placebo at the planned dose and schedule. In the event of study treatment toxicity, dosing may be interrupted, delayed, and/or discontinued. In the event of multiple toxicities, treatment/dose modifications should be based on the worst toxicity observed (CTCAE v5.0) and/or the most conservative recommendation for any given toxicity. Patients are to be instructed to notify Investigators at the first occurrence of any adverse symptom.

All dose holds must be clearly documented in the patient's medical chart and in the CRF. Appropriate follow-up assessments should be done until adequate recovery occurs as assessed by the Investigator.

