9 SCHEDULE OF EVENTS

The Schedule of Events table provides an overview of the protocol visits and procedures. Refer to the Study Procedures section of the protocol for detailed information on each assessment required for compliance with the protocol. The Investigator may schedule visits (unplanned visits) in addition to those listed in the Schedule of Events table in order to conduct evaluations or assessments required to protect the wellbeing of the patient. This Schedule of Events will be followed for the entire study.

Version Date: 11APR2023

Table 1: Schedule of Events

	Screening	On Treatment Period						Post-Treatment Period	
Protocol Activities		Day 1	Day 8	Day 15	Day 22	Day 29	Day 36	EOT (Day 43)	30 days post EOT
Visit Window	(-90 days)		(± 2 days)	(± 2 days)	(± 3 days)	(± 3 days)	(± 3 days)	(+7 days)	(± 7 days)
Informed Consent	X								
Demographics	X								
Medical History	X								
Baseline Characteristics ¹	X								
Eligibility Criteria	X								
Randomization	X								
Clinical Assessments				•	•				
Vital Signs ²	X	X						X	
Physical Exam	X	X						X	
ECOG Score ³	X	X							
NCCN Risk Stratification ⁴	X								
Charlson Comorbidity Index ⁵	X								
Phone Call ⁶			X	X	X	X	X		X
Adverse events		X							
Concomitant Medications		X							

Version Date: 11APR2023

	Screening	On Treatment Period					Post-Treatment Period		
Protocol Activities		Day 1	Day 8	Day 15	Day 22	Day 29	Day 36	EOT (Day 43)	30 days post EOT
Visit Window	(-90 days)		(± 2 days)	(± 2 days)	(± 3 days)	(± 3 days)	(± 3 days)	(+7 days)	(± 7 days)
Laboratory Studies									
Hematology ⁷	X								
Chemistry ⁸	X								
Testosterone	X							X	
Inflammatory marker ⁹	X							X	
Subject Materials									
Patient questionnaires ¹⁰	X							X	
Q-Urol/Placebo dosing diary ¹¹		X						X	
Pain management diary ¹²		X						X	
Study Therapy	•								
Q-Urol/Placebo ¹³					X				
Brachytherapy		X							

¹ Appendix 9.

² Vital signs to include weight and height (height will be measured at screening only), blood pressure, pulse rate and temperature.

³ Appendix 11.

Version Date: 11APR2023

⁴ Appendix 8. NCCN Risk Stratification may be taken from the initial consultation note where brachytherapy was recommended.

⁵ Appendix 10.

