⁶ An appropriately trained and delegated study team member will contact subjects on treatment weekly to assess adverse event and concomitant medication information, to answer subject questions, and to ensure compliance with study medication and procedures. 30 days after the last dose of study drug, a study team member will contact subjects to assess adverse event information.

⁷ CBC with differential and platelets.

⁸ Complete Metabolic Panel including: Sodium, Potassium, Chloride, Carbon Dioxide, Alkaline Phosphatase, Aspartate Aminotransferase, Alanine Aminotransferase, Urea Nitrogen, Glucose, Creatinine, Calcium, Protein, Albumin, Bilirubin, Anion Gap.

⁹ Inflammatory markers include: erythrocyte sedimentation rate, C-reactive protein, prostate-specific antigen (PSA)

¹⁰ Questionnaires include: National Institutes of Health-Chronic Prostatitis Symptom Index (NIH-CPSI), The Expanded Prostate Cancer Index Composite (EPIC), The International Prostate Symptom Score (I-PSS), Rectal Function Assessment Score (R-FAS), The Sexual Health Inventory for Men (SHIM) Questionnaire.

¹¹ A Q-Urol/Placebo dosing diary will be dispensed on the day of brachytherapy and returned completed at the EOT visit (Appendix 6).

¹² Patients will be asked to maintain a diary of the daily use of medications taken for prostate pain for 28 days post-brachytherapy (Appendix 7).

¹³ Q-Urol/Placebo will begin after brachytherapy placement.

Version Date: 11APR2023

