10.3 End of Treatment

An End of Treatment visit will occur six weeks after brachytherapy. At this visit, the patient will discontinue Q-Urol, return any remaining medication, the pain medication diary, and the dosing diary for medication reconciliation. For End of Treatment procedures the Schedule of Events and the Assessments Section.

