16.4.3 Serious Adverse Event (SAE)

Information about all serious adverse events will be collected and recorded. A serious adverse event is an undesirable sign, symptom, or medical condition which:

- Is fatal or life-threatening
- Results in persistent or significant disability/incapacity
- Is medically significant, i.e., defined as an event that jeopardizes the patient or may require medical or surgical intervention to prevent one of the outcomes listed above

Version Date: 11APR2023

• Causes congenital anomaly or birth defect

- Requires inpatient hospitalization or prolongation of existing hospitalization, unless hospitalization is for:
 - Routine treatment or monitoring of the studied indication, not associated with any deterioration in condition (procedures such as central line placements, paracentesis, pain control)
 - Elective or pre-planned treatment for a pre-existing condition that is unrelated to the indication under study and has not worsened since the start of the study drug
 - Treatment on an emergency outpatient basis for an event not fulfilling any of the definitions of an SAE given above and not resulting in hospital admission
 - Social reasons and respite care in the absence of any deterioration in the patient's general condition

Collection of serious adverse events will begin with the initiation of Q-Urol and end 30 days after the last dose study drug or upon initiation of new cancer treatment, whichever happens the soonest.

Any death occurring after the SAE following-up period that is felt to be related to study therapy will be reported according to SAE reporting guidelines.

Toxicities that fall within the definitions listed above must be reported as an SAE regardless if they are felt to be treatment-related or not. Toxicities unrelated to treatment that do NOT fall within the definitions above must simply be documented as AEs in the patient research chart.

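### The single post-treatment safety call may be made up to 7 days early, so scheduled AE questioning can stop 6 to 7 days before the 30-day collection period ends; a plus-only window closes the gap

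*Combined protocol and SAP*

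**What the plan says.** **Collection period.** For adverse events, section 16.4.1 says: "The collection of adverse events will begin after the study drug has been started and end 30 days after the last dose study drug". A parenthesis then allows an earlier end if new cancer treatment is started. For SAEs, section 16.4.3 says collection will "end 30 days after the last dose study drug or upon initiation of new cancer treatment, whichever happens the soonest".

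**Scheduled contact.** In Table 1 (section 9) the only column after EOT is headed "30 days post EOT". It holds a phone call, with a window of ±7 days. The EOT visit itself is on Day 43 with a plus-only window of +7 days. Footnote 6 gives the purpose of the call and a different anchor: "30 days after the last dose of study drug, a study team member will contact subjects to assess adverse event information". The weekly calls do not extend past treatment, because the same footnote says a team member "will contact subjects on treatment weekly to assess adverse event and concomitant medication information".

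**Last dose.** Section 7.4 sets six weeks of therapy starting on the day of brachytherapy, which puts the last dose on Day 42. Section 10.3 ties stopping to the EOT visit: "At this visit, the patient will discontinue Q-Urol, return any remaining medication, the pain medication diary, and the dosing diary". That allows a last dose on Day 43.

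**Other capture routes.** Section 16.4.1 collects "Information about all adverse events, whether volunteered by the subject, discovered by investigator questioning, or detected through physical examination", and goes on to laboratory tests and other means. Section 8 adds: "Patients are to be instructed to notify Investigators at the first occurrence of any adverse symptom".

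**The concern.** The 30-day call is the one scheduled occasion on which anyone asks about the period after treatment. Its window is symmetric, but the period it serves has a fixed end. A call on the plus side can still ask about all 30 days. A call on the minus side cannot, and no second contact is scheduled to cover the remainder. A site can therefore follow Table 1 exactly and still leave the last days of the collection period without a scheduled enquiry.

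What is at stake is the completeness of late AE and SAE capture. Objective 1.2.3 asks whether Q-Urol adds toxicity relative to placebo, and section 13.2.3 tabulates the proportions of patients with adverse events. Section 11.3 makes non-leading questioning of each participant part of the method. With a ±7-day window, the length of the questioned period varies between men for scheduling reasons alone, although the nominal period is the same.

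**Working it through.** The plan gives no figure for this, so there is none to reproduce. The check is day arithmetic.

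**Inputs**
- L = day of last dose: 42 (section 7.4) or 43 (section 10.3 with EOT on Day 43).
- E = day of EOT visit: 43 to 50 (Table 1).
- w = departure of the call from its target: −7 to +7 days (Table 1).
- Collection ends on day L + 30 (sections 16.4.1 and 16.4.3), if no new cancer treatment starts first.

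**Formulas**
- Call day on Table 1's anchor: C = E + 30 + w.
- Call day on footnote 6's anchor: C = L + 30 + w.
- Days without scheduled enquiry: gap = max(0, L + 30 − C).

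**Worst case (w = −7)**

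| Anchor | Last dose | EOT | Earliest call | Collection ends | Gap |
|---|---|---|---|---|---|
| Last dose | L | any | L + 23 | L + 30 | 7 of 30 (23%) |
| EOT | Day 43 | Day 43 | Day 66 | Day 73 | 7 of 30 (23%) |
| EOT | Day 42 | Day 43 | Day 66 | Day 72 | 6 of 30 (20%) |
| EOT | Day 43 | Day 46 | Day 69 | Day 73 | 4 of 30 (13%) |
| EOT | Day 42 | Day 46 | Day 69 | Day 72 | 3 of 30 (10%) |
| EOT | Day 43 | Day 50 | Day 73 | Day 73 | 0 |
| EOT | Day 42 | Day 50 | Day 73 | Day 72 | 0 |

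A call on target (w = 0) or later leaves no gap in any row.

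**Average.** The documents do not say how calls will spread over the window. Assume they are uniform over the 14 days from −7 to +7.
- Last-dose anchor, or EOT and last dose both on Day 43: 7² / (2 × 14) = 49 / 28 = 1.75 days, or 1.75 / 30 = 6%.
- EOT anchor, EOT Day 43, last dose Day 42: (7 − 1)² / 28 = 36 / 28 = 1.29 days, or 1.29 / 30 = 4%.

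Now assume also that EOT is uniform over Days 43 to 50, keeping Table 1's anchor and the last dose where it was:
- Last dose Day 43: (1/7) × (7³ / 3) / 28 = 343 / 588 = 0.58 days, or 2%.
- Last dose Day 42: (1/7) × (6³ / 3) / 28 = 72 / 196 = 0.37 days, or 1%.

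The shrinkage with a later EOT holds only on Table 1's anchor and only if dosing does not run on to the later visit. On footnote 6's anchor the worst case stays at 7 days whatever the EOT date.

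**After the fix.** If the call cannot precede day L + 30, then C ≥ L + 30 and the gap is 0.

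**The case against.** The best defence is that a ±7-day window is ordinary scheduling tolerance around a target that footnote 6 sets correctly, at 30 days after the last dose. The plan does not contradict itself on the target date. That is fair, and it is why this is an improvement to the schedule rather than an error. It does not answer the narrower point: on a call that closes a fixed period, the minus side removes coverage and the plus side does not.

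Four stronger readings are tempting, and the documents do not support them.

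- *A reader might infer that events after an early call are lost, or are caught only if the man volunteers them.* Section 16.4.1 also collects events found by questioning, examination, laboratory test or other means, and section 8 has patients told to report symptoms. An early call ends scheduled enquiry, not collection or SAE reporting.
- *A reader might infer that the safety denominators are wrong.* Section 13.2.3 tabulates counts and proportions of patients, and section 12.3.1 defines the toxicity population by receipt of one dose. No rate per unit of follow-up time is planned. A man's entry changes only if his first event of a type falls in the last few days after an early call and reaches the site by no other route.
- *A reader might infer bias between arms.* The window is the same in both arms and the trial is double-blind, so nothing in the text points to a differential effect.
- *A reader might infer that every man is exposed.* Collection also ends when new cancer treatment starts. Under section 7.1, HDR is always followed by external beam radiation and LDR sometimes is, in each case after the study drug regimen. The text does not say whether this planned radiation counts as new cancer treatment. If it does, collection may close before day 30 for those men and the gap may not arise. Men on LDR alone would still be exposed.

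**Conclusion.** The mismatch is real and small. AEs and SAEs are collected to 30 days after the last dose, while the only scheduled later contact may lawfully be made up to 7 days early. The worst case is 7 of 30 days (23%) on the last-dose anchor, or 6 of 30 days (20%) with EOT on Day 43 and the last dose on Day 42. It should not be read as the typical loss. With EOT on Day 43 and calls spread evenly, the average is 1.29 to 1.75 days; with EOT also spread evenly over Days 43 to 50, it is 0.37 to 0.58 days. Both averages rest on assumed uniform timing, which the documents neither state nor rule out.

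The effect is limited to the completeness of scheduled questioning about late safety events. The primary endpoint, sample size, power and Type I error are not affected. This is a cheap improvement.

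**What to change.** In Table 1, change the window of the post-treatment safety call from ±7 days to 0 to +7 days, counted from day 30 after the last dose. This also reconciles Table 1's EOT anchor with the last-dose anchor in footnote 6 and section 16.4. Add to footnote 6 that the caller asks about events through day 30 after the last dose, however late in the window the call is made.

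While the text is open, two neighbouring points merit a sentence each: whether planned external beam radiation counts as new cancer treatment for sections 16.4.1 and 16.4.3, and how the off-study criterion in section 7.4.2, met at the completed EOT visit, fits with a call 30 days later. The fix does not depend on either.

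The cost is one table entry and one footnote sentence. No contact, staff or data item is added. The downside is that some calls are made a few days later than they would have been.
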